8.1.2 Control intervention

The control area that remains blanco is measured according to the same protocol.

8.1.3 Packaging, labeling and use

The products are purchased fresh and are within the expiration date. The opening date is noted on the tube.

8.1.4 Storage

The storage of the product is carried out in accordance with the package leaflet.

8.2 Administration of the experiment

Since no prescription drugs or invasive methods are used, the experiment is not discussed further in chapters 8.2-8.4 and only chapter 9 is referred to.

8.2.1 Experimental intervention

The intervention consists of a topical application of either a warming product or a cooling product. The area of application is in the lumbar back area, paravertebral on one side on an area of 10cm x 10cm.

8.2.2 Control intervention

The control intervention does not consist of any application, the selected skin area remains blanco. The lumbar paravertebral opposite side of the intervention site is taken as a control skin area.

8.3 Dosage, application modification

Exactly the same amount of product is used per subject, 3g. The product is stored at room temperature, weighed and then applied to the application surface with a glove and spread until it can no longer be spread further.

Local change in skin characteristics during and after a topical application of a warming or cooling product Version
04-24.06.2019 Side 35 from 53

SUPSI

8.4 Adherence to the study intervention

The test subjects are neither motivated nor unnecessarily distracted by the examiners or the study director with conversations. Communication is kept to a minimum, only study-related discussions are held in order not to influence the physiological effects and to ensure homogeneity.

8.5 Follow-up treatment of eliminated participants

Data already collected from eliminated participants will be destroyed and will not be included in the data analysis of the study.

There is no disadvantage for the participants if they discontinue their participation in the study and no further interventions are necessary for follow-up treatment.

If study participation was discontinued due to an excessive skin reaction occurring during study participation, this will be recorded and reported to the sponsor investigator (head of the research laboratory), study leader and supervisor of the study. If medical care is necessary, the report is forwarded to the business liability insurance of Thim van der Laan AG (Basler Versicherung) in order to ensure the appropriate follow-up treatment.

8.6 Preventive measurements

The questionnaire asks about the intake of medication, injuries and operations, as well as known relevant diseases and allergies. In addition, a skin discrimination test is carried out in the area of application. Pregnant women or nursing mothers are not allowed to participate in the study. The test subjects must present a negative pregnancy test (provided free of charge by us). The test result is noted on the health questionnaire. Only then are the screening tests (skin discrimination test, product compatibility) carried out.

8.7 Accompaniments

No further side effects are expected from study participation.

8.8 Liability

The experiments take place exclusively in the research laboratory of the "Thim van der Laan" University College Physiotherapy in Landquart. This means that there is no transport of the products, equipment or test persons used. There is therefore no liability for transport.

8.9 Return of the medical device

Only as many over-the-counter topical applications are purchased as are needed. A return is neither necessary nor provided for.

SUPSI

9 STUDY STRUCTURE & EVALUATION

9.1 Schedule Study Protocol

1. **Contact by e-mail, then by phone by the director of studies**
 - a. Rough explanation of the study
 - b. Announcement of the inclusion and exclusion criteria, corresponding examination of the suitability of the test persons
 - c. If interested and suitable, delivery of further documents (see point 2)
2. **Subject information, declaration of consent**
 - a. Clarify possible questions
 - b. If the subject agrees, make an appointment for screening tests
3. **On-site explanations plus screening tests (pregnancy test (for women only), skin discrimination test, product skin compatibility), 1st day of contact**
 - a. Time required 30min
 - b. If the test person is suitable and consented, sign the declaration of consent and make an appointment for the actual measurement
4. **Measurement day on site, 2nd contact day**
 - a. 30min (cleansing of the skin in the application area and 20-minute room acclimatization, marking of the application area and adjustment of the measuring equipment)
 - b. Executing the test protocol (see Intervention)

Intervention

- Baseline measurement:	1min
- Application of topical product:	1min
- Follow-up measurement time 0min:	1min
- Follow-up measurement time 10min:	1min
- Follow-up measurement time 20min:	1min
- Follow-up measurement time 30min:	1min
- Follow-up measurement time 40min:	1min
- Follow-up measurement time 50min:	1min
- Follow-up measurement time 60min:	1min

Total Time Expenditure Intervention: approx. 100 min

The total time required for both contact days together results in a duration of 130 minutes per test subject.

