Preparation	
Subject recruitment
 
The subject information and declaration of consent are submitted. Questions may be asked. If the subject agrees with the information, he or she will be summoned to the first day of contact. This includes the explanations on site, the signature of the declaration of consent, the completion of the health questionnaire and the screening test. This includes a skin discrimination test both epicritically and protopathically (warm-cold, pointed-blunt, sense of vibration) of the lumbar back area paravertebral on both sides. If the test is passed, a possible skin intolerance to the products to be applied is ruled out. For this purpose, a small product sample is applied to the volar forearm and the reaction is waited for during 10 minutes of post-application. If excessive redness and/or itching, pain, uticalia occurs, the subject will be excluded from the study. The pregnancy test must be negative (women only). If all tests are passed, an appointment is made for the intervention. The subject must follow the following rules: do not apply body lotion to the back, do not consume any meal or drinks (coffee / tea / alcohol – water allowed) 2 hours before the appointment⁹.
 
Test Subject Preparation Measurement Day
 
The test subject lies topless in a prone position on a treatment table, women in bras. First, the lumbar back area is rubbed on both sides with distilled water (room temperature) and a soft cotton cloth with light pressure. This is followed by the 20-minute room acclimatization phase in the same storage¹⁰. The room temperature is kept as constant as possible (deviation of $\pm 2^{\circ}\text{C}$), the window blinds and windows are closed, and the ceiling lighting is minimal.

--------------------	---

SUPSI

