2.7 Patient information and informed consent

The examiners will explain to each participant individually the nature of the study, its content, intent and objective. This includes the protocol flow, approximate time duration, possible risks and benefits. The participant is informed that participation is voluntary and can be withdrawn from the study at any time, without personal consequences of any kind. The participant will be informed about data protection, the handling of personal data and their access.

Each participant receives written subject information and the declaration of consent with the detailed study description and all necessary information to be able to decide whether to participate in the study. The participant will also be given sufficient time to read this written information and to ask questions to the responsible examiners.

The subject information and the informed consent form are submitted to the CEC, where they must be reviewed and approved.

The signed declaration of consent must be submitted before the start of the study process. The participant should read them before signing and check their contents. The responsible examiner then also signs the declaration of consent. Finally, the participant receives a copy of the declaration of consent. The signed declaration of consent is kept in the original as a study document in a locked filing cabinet.

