9.2 Procedure at each visit of the test subjects

9.2.1 Single measurement

The project involves multiple visits. After contacting them by telephone and announcing the inclusion and exclusion criteria, the subject information and the declaration of consent are submitted for inspection and reading. If the subject agrees with the study conditions and criteria, he or she registers to make an appointment for the 1st contact day. The 1st contact day includes, in the order described, the; Explanations on site, signing the declaration of consent, filling out the health questionnaire, carrying out the screening tests (including pregnancy test for female subjects). If the subsequent screening tests have been passed, an appointment is made for the actual measurement day (2nd contact day).

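### Section 9.1 step 3b places the consent signature after screening tests that include product on the skin, contradicting sections 2.7, 9.2.1 and the synopsis

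*Combined protocol and SAP*

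**What the plan says.** Section 9.1 (Schedule Study Protocol) sets out four numbered steps. Step 3 is the first contact day: "On-site explanations plus screening tests (pregnancy test (for women only), skin discrimination test, product skin compatibility), 1st day of contact". Its item b reads: "If the test person is suitable and consented, sign the declaration of consent and make an appointment for the actual measurement".

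Three other places deal with when consent is signed:
- Section 2.7: "The signed declaration of consent must be submitted before the start of the study process".
- Section 9.2.1, which says it lists the first contact day in order: after the explanations come "signing the declaration of consent, filling out the health questionnaire, carrying out the screening tests".
- Study Synopsis, Preparation: "This includes the explanations on site, the signature of the declaration of consent, the completion of the health questionnaire and the screening test".

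Screening involves product on the skin. According to the synopsis, "a small product sample is applied to the volar forearm and the reaction is waited for during 10 minutes of post-application". Sections 3.7 and 9.1.5 describe the same forearm test.

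On the pregnancy test, section 8.6 requires a negative result, has it noted on the health questionnaire, and continues: "Only then are the screening tests (skin discrimination test, product compatibility) carried out". The synopsis describes the forearm sample and exclusion for a reaction, and then says: "The pregnancy test must be negative (women only). If all tests are passed, an appointment is made for the intervention". Section 9.2.1 includes the pregnancy test among the screening tests without giving its position. Section 9.1.5 attaches it to the health questionnaire.

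**The concern.** Under step 3b a person signs if found suitable, and section 8.1.1 makes passing the product and skin discrimination tests a condition of admission. The condition for signing therefore cannot be met until the tests have been done. Anyone who follows 9.1 literally would carry out study procedures, including a product exposure, without a signed form. A person who reacts to the sample would be unsuitable and would never sign, although exposed.

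What is at stake is participant protection and compliance with the plan's own consent rule. The synopsis also commits the study to ICH-GCP and the Declaration of Helsinki.

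The position of the pregnancy test matters because section 10.3.1 lists pregnancy among the package-leaflet restrictions. That section says vulnerable people are identified before the actual product application, but not whether the forearm sample counts as one.

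**Working it through.** No figure is involved, so the check is a comparison of the stated orders.

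| Place | Consent signature | Pregnancy test |
|---|---|---|
| 2.7 | Before the study process starts | Not addressed |
| Synopsis, Preparation | Before questionnaire and screening test | Mentioned after the forearm sample, with no order word |
| 8.6 | Not addressed | Explicitly before skin discrimination and product tests |
| 9.1 step 3 | After screening, for those found suitable | Listed first of the three screening tests |
| 9.1.5 | Not addressed | Attached to the health questionnaire |
| 9.2.1 | Before questionnaire and screening tests, as a declared order | Among the screening tests, position not given |

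1. **Consent.** Three places put the signature first and one puts it after screening. The late signature in 9.1 does not rest on the position of item b alone. It follows from the condition of suitability and from the pairing with the appointment for the measurement day, which the synopsis and 9.2.1 make only once screening has been passed.

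2. **What precedes the signature under 9.1.** The pregnancy test (women), the skin discrimination test and the forearm sample with its 10-minute wait. The 3 g study application is on the second contact day, after the signature in every version.

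3. **Pregnancy test.** Section 8.6 fixes an order. The synopsis gives only a condition, placed later in the narrative. The list in 9.1 agrees with 8.6 as far as a list can. This is a difference in clarity more than a direct contradiction.

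4. **Both safeguards together.** Product precedes the signature only under 9.1, and precedes the pregnancy test only under the narrative order of the synopsis. In 9.1 the pregnancy test is listed ahead of the product test; in the synopsis the signature comes ahead of screening. No single section places product before both.

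5. **Whom a correction can still reach.** The plan has 90 main-study participants, 45 warming and 45 cooling, plus 15 for the sub-analysis: 90 + 15 = 105. Version 04 is dated 24.06.2019. The schedule puts warming-product data collection in 2017, cooling-product collection in March to October 2019 and the sub-analysis in September and October 2019. If the 45 warming participants were complete by then, new wording could reach between 15 (all cooling participants already screened) and 45 + 15 = 60 (none yet screened) measured participants, plus screening failures, whose number is not given.

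**The case against.** The strongest reply is that the plan's rule is already consent first. Section 2.7 uses mandatory language. Section 9.2.1 sits under the heading for procedures at each visit, and it is the only text that declares its list to be a sequence. Section 9.1 is then one loosely worded summary line; item a of the same step is merely a duration, so the letters are not strictly chronological. The mention of consent in 3b could refer to agreement given in step 2, and the study process in 2.7 could be read as starting on the measurement day.

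Most of this stands as a limit on the point. It shows that 9.1 is the outlier and that the plan as a whole does not intend exposure before consent. It does not remove the contradiction. Agreement in step 2 is not a signature, and 3b still puts the signing after suitability is known. A late start for the study process in 2.7 would leave the conflict with 9.2.1 and the synopsis untouched.

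The reply is stronger on the pregnancy test. Sections 8.6 and 9.1.5 tie it to the health questionnaire, which the synopsis lists before the screening test, so the synopsis can be read consistently with 8.6.

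A reader might infer four stronger things that the documents do not support:
- **That product exposure may precede both consent and the pregnancy result.** This requires taking consent from 9.1 and the pregnancy test from the synopsis, and ignoring 2.7, 8.6 and 9.2.1.
- **That 9.1 is the list staff work from.** No section says so.
- **That data from affected participants may be unusable.** Even under 9.1, everyone measured signs on the first contact day, before any outcome measurement, and screening failures contribute no outcome data.
- **That at least all 105 participants are affected.** This assumes 9.1 always overrode the contrary sections; the pregnancy question also concerns women only.

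**Conclusion.** The contradiction on consent is real and should be corrected. Section 9.1 step 3b, followed literally, breaches the plan's own rule in 2.7 and conflicts with 9.2.1 and the synopsis. The consequence is study procedures and a small forearm exposure before signature, and no signature at all from people who fail screening. The pregnancy-test inconsistency is secondary and weaker; it calls for one stated position, not a finding of error in any one section.

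The size is limited. The wording covers everyone screened, but the documents give no count of people handled in the wrong order and no evidence that there were any. No effect on the primary or secondary results follows. The conclusion rests on reading suitability in 3b as the outcome of the screening tests, which section 8.1.1 supports. The 15 to 60 range for those a correction could reach rests on the published schedule having been kept.

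**What to change.** Rewrite section 9.1 step 3 so that the signature comes before the screening tests, as 2.7 and 9.2.1 already require, and leave only the appointment for the measurement day conditional on suitability. Then reconcile the synopsis (Preparation), 8.6, 9.1, 9.1.5 and 9.2.1 into one stated sequence for the first contact day, including where the pregnancy test falls relative to the forearm sample. That placement is for the sponsor and investigator to settle; the review asks only that every section state the same one.

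The cost is protocol wording, handled through the amendment route in section 2.10. No visit, test or form is added, and the analysis is unchanged.

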9.1.1 Measurement of primary and secondary results

Measurements of perfusion of skin microcirculation, erythema formation, skin surface temperature, oxygen saturation of the muscles and recording of subjective temperature perception can be performed within one minute.

9.1.2 Measurement of primary results

The primary measurements refer to the area of application, lumbar back area, right-sided or left-sided paravertebral depending on randomization.

SUPSI

Perfusion of skin microcirculation

The perfusion of the skin microcirculation is measured using the Laser Speckle Contrast Imager and the X-Flow ultrasound.

Erythema formation

The erythema formation is visualized by means of the chromameter.

Skin surface temperature

The surface temperature of the skin is measured by means of an infrared thermometer and the i-buttons. In addition, a thermal imaging camera records the skin surface temperature.

Oxygen saturation of the superficial muscles

The oxygen saturation of the superficial muscles is determined using the Moxy (Muscle Oxygen Sensor).

Subjective Perception Parameters

The test subjects indicate their subjective temperature perception on a 9-point scale from -4 (very cold) to +4 (very hot). They then rate the thermal comfort on a 5-point scale between 0 (pleasant) and 4 (extremely uncomfortable).

9.1.3 Measurement of secondary results

The measurement of the secondary results concerns the tissue directly surrounding the application area. The measurement method remains identical.

9.1.4 Collection of further results

No further results will be collected.

9.1.5 Collection of safety parameters

Apart from the health questionnaire (including pregnancy test for female subjects), the ability to discriminate against the skin and a skin compatibility test (product application in a small area on the volar forearm), no safety parameters are collected.

9.1.5.1 Unfavorable events

In the event of an allergic reaction, the experiment is stopped immediately.

9.1.5.2 Laboratory parameters

-

9.1.5.3 Vital signs

-

9.1.6 Collection of data in case of early termination of studies

For the participants, there is no disadvantage in the event of an (arbitrary) discontinuation of study participation and no further interventions are necessary for follow-up treatment. The data collected to date will be evaluated as far as possible and included in the data analysis (in accordance with Art. 9 ClinO).

SUPSI

However, if study participation was discontinued due to an excessive skin reaction occurring during study participation, this will be recorded and reported to the sponsor investigator (head of the research laboratory), study management and supervisor of the study. In the event of necessary medical treatment, the report is sent to the business liability insurance of Thim van der Laan AG (Basler Versicherung).

The following are recorded:

- Date and time of the incident
- Course of the incident
- Persons involved & witnesses
- Study ID (specified by the CEC)
- Personal data of the person concerned (if not previously recorded)

9.2 Procedure at each visit of the test subjects

9.2.1 Single measurement

The project involves multiple visits. After contacting them by telephone and announcing the inclusion and exclusion criteria, the subject information and the declaration of consent are submitted for inspection and reading. If the subject agrees with the study conditions and criteria, he or she registers to make an appointment for the 1st contact day. The 1st contact day includes, in the order described, the; Explanations on site, signing the declaration of consent, filling out the health questionnaire, carrying out the screening tests (including pregnancy test for female subjects). If the subsequent screening tests have been passed, an appointment is made for the actual measurement day (2nd contact day).

9.2.2 Multiple visits

1. On-site explanation and screening tests, 1st contact day

The subjects will be comprehensively informed about the process and possible risks before they are confirmed to participate in the study. You will also receive the information in written form and have the opportunity to ask questions. In the declaration of consent, they are explained what their rights and obligations are when participating and that they may withdraw from participation at any time without giving reasons, without incurring any disadvantages as a result. More detailed information can be found in chapter 2.7. In addition, a screening is carried out during the first contact in order to check the skin's ability to discriminate and to detect skin intolerances to an ingredient of the topical products to be applied at an early stage. An initial selection process of suitable test persons takes place.

2. Measurement, 2nd contact day

2.1 Preparation of the subject

The test subject lies with his upper body undressed for the men, women in a bra in a prone position on a treatment table. The lumbar back area is washed with distilled water (room temperature) and a soft cotton cloth to remove possible skin and fat residues. An alcohol solution is deliberately avoided so as not to influence the temperature perception of the test subjects. This is followed by a 20-minute room acclimatization to prepare the test subject for the measurements. The area of application (10cm x 10cm, paravertebral lumbar, randomized triggered) is drawn and the measuring apparatus is adjusted. This is followed by the baseline measurement.

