
Measurements and procedures:
	
After the 20-minute acclimatization phase, the application area is drawn (skin-friendly pen), the template (recess 10cm x 10cm) is applied and the baseline measurements (a-e) are performed. After the baseline measurement, the product is applied (3g)⁸. The product is applied until it can no longer be distributed. The research employee wears a glove. This is followed by the measurements (a-d) at 0min, 10min, 20min, 30min, 40min, 50min, 60min post-application.
 
a) Perfusion of skin microcirculation
 
The perfusion of the skin microcirculation is performed using the Laser Speckle Contrast Imager (moorFLPI 2, moor instruments, www.moor.co.uk), the High Power Laser Doppler (moorVMS-LDF1-HP, moor instruments, www.moor.co.uk) and the ultrasound X-Flow (esaote MyLabClassicC, Maastricht, Netherlands, www.esaote.com). Since the contact gel, which is required for the ultrasound X-Flow measurement, could interfere with the product application, or could interfere with the subjective temperature perception of the subject, the ultrasound measurement is only measured at the time of baseline and 60min post-application. This was after questioning the subjective parameters.
 
b) Erythema formation
 
Erythema formation is visualized using the chromameter (www.konicaminolta.eu). The chromameter measures the light reflection and absorption of the skin.
 
c) Skin surface temperature
 
The surface temperature of the skin is measured using an infrared thermometer (Votcraft InfraRed Thermometer, IR 800-20D) and the i-buttons. The iButton system consists of self-adhesive sensors that wirelessly transmit skin temperature information to a computer (www.ibuttonlink.com). In addition, a thermal imaging camera (www.csem.ch) records the skin surface temperature.
 
d) Oxygen saturation of the superficial muscles
 
The oxygen saturation of the superficial muscles is determined using the near-infrared measurement method (moorVMS-NIRS, moor instruments, www.moor.co.uk) The measurement is non-invasive and painless. The sensors are placed on the corresponding muscles.
 
e) Subjective Perception Parameters
 
The test subjects indicate their subjective temperature perception on a scale of 9 points from -4 (very cold) to +4 (very hot). They then rate the thermal comfort on a 5-point scale between 0 (pleasant) and 4 (extremely unpleasant)¹¹.
 
Further processing of the data
 
Windows uses Excel for data pooling and the graphical representation of the end data®.

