6.1.2 Blinding

Blinding of the subjects is possible with regard to the topical application of warming versus cooling, but not with regard to the control area, which remains blanco.

It is not possible to blind the applicator, but it is possible to blind the assessor of the primary and secondary results.

In addition, the blinding of the statistician can be guaranteed, who has no access to the personal data of the test persons and is not present during the data collection.

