7.3 Group assignment

The group allocation (warming product, cooling product) is concealed by means of a lot in a sealed envelope, which is drawn under the supervision of the study leader. The product to be applied and the side of the application area are noted on this lot. The examiner determines the examination condition and only passes on the subject number to the assessor. At the end of the entire data collection, the auditor pools the data sets according to the application.

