11.4.2 Primary Analysis

The statistical data analysis will be carried out by [name] after completion of the data collection of the entire project.

Repeated measures analysis of variance (MANOVA)

2 factors:

Factor 1: Intervention (warming product versus control / cooling product versus control)

Factor 2: Time (baseline, 0min, 10min, 20min, 30min, 40min, 50min, 60min postal application)

The significance level is set at $P < 0.05$, and the statistical data analysis is carried out with SPSS V. 23.

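### The randomised side is marked on the skin before the baseline reading, so assessor blinding to side is not secured at baseline, which is a level of the time factor in the only planned analysis

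*Combined protocol and SAP*

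**What the plan says.** - **Order of steps.** Section 9.2.2, under Preparation of the subject, says that the randomised application area "is drawn and the measuring apparatus is adjusted. This is followed by the baseline measurement". The synopsis (Measurements and procedures) agrees and adds the template: "the application area is drawn (skin-friendly pen), the template (recess 10cm x 10cm) is applied and the baseline measurements (a-e) are performed". In section 9.1, marking is in step 4a, and the test protocol, which starts with baseline, is step 4b. All three place application of the product after baseline.
- **What the lot contains.** Section 7.3: "The product to be applied and the side of the application area are noted on this lot". No section says when the envelope is opened.
- **Blinding.** Section 6.1.2 says that "it is possible to blind the assessor of the primary and secondary results". Section 7.3 gives the mechanism: "The examiner determines the examination condition and only passes on the subject number to the assessor". Subjects can be blinded to warming versus cooling, "but not with regard to the control area, which remains blanco".
- **Control area.** Section 8.1.2 has it measured under the same protocol. No section says that it is outlined or covered with the template.
- **Analysis.** Section 11.4.2 plans one two-factor repeated-measures analysis (intervention, time), with "Factor 2: Time (baseline, 0min, 10min, 20min, 30min, 40min, 50min, 60min postal application". Section 11.4.3 plans no secondary analysis. The hypotheses in section 11.1 compare change with the opposite side, which implies a side-by-time contrast, although the interaction is not named as the test.

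**The concern.** Baseline is the one reading at which both sides are untreated and look alike, so it is the one reading at which the assessor could readily be kept unaware of the side. The written order gives this up without need.

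Two routes to a side-specific shift follow. The first is knowledge: someone who sees which side is outlined may read or record the two sides differently. Section 12.2.1 shows where there is room for this. Chromameter and infrared thermometer values are read from a display and copied by hand, and the ratings are asked orally. Laser speckle, ultrasound, i-button, thermal camera and muscle oxygen data go through software, which leaves less room. The second is physical: pen and template contact is described only for the application area, just before the baseline readings. Section 5.1 itself treats contact with the measured skin as a disturbance when it compares the oxygen sensors.

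At stake is the validity of the side-by-time comparison. The planned analysis cannot tell a shifted baseline from a real change after application.

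**Working it through.** **1. Is the side exposed at baseline?** The area drawn before baseline is the randomised one (section 9.2.2), and the side is written on the lot (section 7.3). Whoever draws the outline must therefore have the side from the lot by then. This is an inference, though close to a necessary one. Passing on only the subject number can keep the product from the assessor. It cannot hide an outline on the skin being measured, unless the other side carries the same outline.

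**2. How does a baseline shift enter the analysis?** Let D(t) be the treated-minus-control difference at time t, with no product effect. Add d to the treated side at baseline only. Then D(t) − D(baseline) moves by −d at each of the 7 later times. A shift common to both sides leaves D unchanged. A side-specific shift that is constant over all 8 times leaves the changes unchanged. Only a shift that differs between sides and over time matters.

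**3. Inputs.**
- 8 time levels and a 5% significance level (section 11.4.2).
- n = 45 per product type (synopsis).
- There is no planning calculation to reproduce. Section 11.2 gives no effect size, SD or power; only the total can be checked: 45 + 45 + 15 = 105, as stated.
- Assumed: d, in units of the residual SD of the side difference at one time point, and sphericity.

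**4. Formula.** The noncentrality of the side-by-time test is λ = n·d²·(1 − 1/8).
- d = 0.2: λ = 45 × 0.04 × 0.875 = 1.575
- d = 0.3: λ = 45 × 0.09 × 0.875 = 3.544

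The plan's label covers both a univariate repeated-measures test, F with 7 and 7 × 44 = 308 degrees of freedom, and a multivariate test, F with 7 and 45 − 7 = 38. Both are shown.

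**5. False-positive rate at n = 45, no product effect.**

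| Baseline-only shift d | Univariate | Multivariate |
|---|---|---|
| 0 | 5.0% | 5.0% |
| 0.1 | 6.4% | 6.2% |
| 0.2 | 11.5% | 10.5% |
| 0.3 | 22.0% | 19.1% |
| 0.5 | 59.4% | 51.7% |

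Simulation of the univariate test (4,000 runs) gave 4.8% at d = 0, 22.6% at 0.3 and 59.3% at 0.5. With 0.3 added to both sides it gave 4.9%, which confirms that a common shift cancels.

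**The case against.** The strongest objection is that the modelled bias may not be the natural one. The side stays known at all later readings, because the product is on one side only and the subject cannot be blinded to the untreated side. A reading tendency tied to the known side might act at all 8 times and then cancel: a simulation at n = 45 with 0.3 SD at every time gave 4.8%. Conceal baseline alone, and the same tendency acts at the 7 later times only, giving 22.1%, about the same as for baseline only. The arithmetic is right. But the cancelling case needs a constant side-linked bias that is already at full size before any product is on the skin. Expectation about the product's effect is the more plausible source, and that would differ before and after application. The objection therefore does not make a concealed baseline a real trade-off. What stands is that later readings remain unprotected.

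Other parts also stand. The documents do not say when the lot is opened, and they do not say that the control area is unmarked. The shift sizes are assumptions. Temperature is also measured by two instruments that are not hand-copied.

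A reader might infer that the whole allocation, product and side, is known to the assessor at baseline. The documents do not support this: section 7.3 withholds the product. The schedule in Table 1 (warming products in 2017, cooling in 2019) may let the product class be guessed from the date, and changing the order of marking would not alter that. A reader might also infer that any shift at baseline creates a false effect; step 2 of the working shows that it must differ between sides.

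**Conclusion.** The point holds for side, at baseline. The randomised side is marked before baseline in three places, nothing describes how the mark is hidden from the assessor or matched on the control side, and baseline is part of the outcome in the only planned analysis. The assessor blinding that section 6.1.2 calls possible therefore has no working mechanism for side at the one time when it could readily have one.

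As an illustration, a side-specific, baseline-only shift of 0.2 or 0.3 SD at n = 45 would take the nominal 5% to about 11% or 20%. This rests on the assumed shift, sphericity, no product effect, and the side-by-time interaction being the test. It should not be read as evidence that baseline values are biased, or as an estimate of the trial's actual error rate. The documents support neither. Exposure is greatest for the chromameter, the infrared thermometer and the oral ratings.

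It is worth correcting because the protection is standard and cheap, not because harm has been shown.

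**What to change.** - **Synopsis (Measurements and procedures), section 9.1 step 4 and section 9.2.2:** mark both paravertebral areas identically, using the same template on both; record baseline on both sides with all instruments and ratings; then open the sealed lot and apply the product to the side it names.
- **Section 7.3:** state that the lot is opened only after the baseline values are recorded. The protocol does not say whether the forearm compatibility test on the first contact day uses the allocated product. If it does, side and product need separate envelopes, so that the side can stay sealed until then.
- **Section 6.1.2:** say that blinding to side is secured at baseline, and what, if anything, protects later readings.

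**Cost.** One more outline, a few seconds between baseline and application, and an amendment reviewed by the ethics committee (section 2.10). Table 1 has the warming data collected in 2017 and cooling data collection starting in March 2019, before this version of 24.06.2019. Measurements already taken keep the old order, so the order used should be recorded for each subject.

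**Limit.** The change protects baseline only. Later readings remain open to knowledge of the side.
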